7.6 Unscheduled Visit

Participants will be invited to return to the PRW for any needed medical care in the interim between discharge from the ward and the final study visit at 12 months (\pm 14 days) post-randomization. Any unscheduled visit will be recorded in the participant CRF and may be recorded as an AE or SAE if appropriate.

8 STUDY PROCEDURES/EVALUATIONS

8.1 Clinical Evaluations

History: A brief medical history pertaining to the immediate clinical condition is obtained immediately on arrival to the PRW. More detailed medical history is obtained after the participant has been stabilized. History includes a history of the immediate illness, previous similar illnesses, and a brief developmental history. History is obtained by interview and supplemented by any records in the participant's health passport.

Medication history is obtained on admission to the PRW and recorded on the same enrollment form. This history relies heavily on the written record provided in the health passport of the participant.

Physical Examination: A full physical examination is performed on arrival to the PRW and after immediate stabilization. Specific vital signs and organ systems evaluated can be found on the physical exam CRF). Twice daily after consent, a targeted physical exam is conducted by a study physician. The results of these daily examinations are recorded in free form on the continuation sheets. At minimum these exams will evaluate the neurologic status of the participant (as determined by BCS), examination of the heart, lungs, liver, and spleen.

Vital Signs: Vital signs (temperature, pulse rate, blood pressure, respiratory rate, oxygen concentration, and BCS) will be evaluated and recorded by a dedicated study nurse every two hours until the participant regains consciousness (BCS \geq 3).

Table 6. Blantyre Coma Score (maximum = 5):

Motor Response	Verbal Response	Eye Movements
Nil/extend	0	Nil/gasp 0
Withdraw	1	Abnormal cry 1
Localize	2	Normal cry or speech 2

Table 7. Modified Blantyre Coma Score (for intubated patients, maximum = 5):

Motor Response	Verbal Response	Eye Movements
Nil/extend	0	Nil/gasp 0
Withdraw	1	Attempt to cry, grimace 1
Localize	2	Clear mouthing of words around ET tube 2

IV anti-malarial therapy: Artesunate will be administered according to national treatment guidelines upon admission, at 12- and 24-hours post-admission, once a day thereafter until the child is able to take oral medication, or for a total of 5 days.

Oral anti-malarial therapy: After the child is able to take oral medications, they will be prescribed Co-Artem® (a fixed dose combination tablet containing artemether, 20 mg and lumefantrine, 120 mg). Dosing will be weight-based, in accordance with national treatment guidelines. Oral therapy is for three days.

Malaria parasite (MP) and packed cell volume (PCV): An evaluation of malaria parasitemia (MP) and hematocrit (packed cell volume (PCV)) will be performed at initial screening and every six hours thereafter. These exams will continue until two consecutive examinations show an absence of malaria parasites. MP evaluation is performed on a thick blood smear. PCV is determined in a microhematocrit tube. Blood for both of these exams is obtained by fingerprick.

Lactate and glucose check: Blood lactate and glucose levels will be measured at the bedside using point-of-care tests. They will be evaluated on admission and every 6 hours thereafter until the participant has maintained a BCS of 3 for greater than 4 hours.

Lumbar puncture: Participants will be placed in the decubitus position, the L3-4 spinal interspace determined by palpation, and the skin cleaned three times with alcohol. A twenty-one-gauge needle will be used in the procedure. Four ml (\pm 2 ml) of spinal fluid will be obtained. If at least 4 ml is obtained, 1 ml will be sent for each of culture and sensitivity, cell count plus differential, and protein and glucose determinations. 1 ml of spinal fluid will be archived for determination of biomarkers of increased brain volume.

Retinal exam: Fundoscopy will be performed at admission and every 24 hours thereafter until the patient reaches a BCS of 3 for greater than 4 hours. Pupils of participants will be dilated with mydriatics (a combination of 1.0% tropicamide hydrochloride and 2.5% phenylephrine hydrochloride) in both eyes. A trained clinician will perform direct and indirect ophthalmoscopy on fully dilated eyes.

MRI: After consent for screening is obtained and medical stabilization has occurred, brain MRI images will be obtained.

ONSD: Measurement of optic nerve sheath diameter is being investigated as a non-invasive measure of increased brain volume. The procedure takes 10-15 minutes to perform. A small amount of ultrasound gel is placed on the eyelid and the probe gently pressed superior to the globe. The procedure will be repeated daily until the child maintains a BCS of 3 for four hours.

Transcranial Doppler: TCD examination will be performed at enrollment and every 24 hours thereafter while the patient is hospitalized. Middle cerebral arteries (MCAs), extracranial internal carotid arteries (EC-ICAs), and basilar arteries (BAs) will be insonated at 1 mm intervals using the transtemporal or occipital acoustic windows. Systolic (Vs), diastolic (Vd), mean flow velocities (Vm) and pulsatility index (PI) will be recorded at each interval. Based on findings of TCD examinations, subjects will be placed into phenotypic groups.

Neurological exam: A focused neurological examination will be performed at admission, and at 0800 and 1600 daily (\pm 2 hours) while the patient is comatose (BCS \leq 2). A detailed neurological examination will be performed at each of the 1, 6, and 12 month (\pm 2 weeks) post-randomization follow-up visits. While hospitalized, the examination will focus on candidate neurological exam markers of increased brain volume: restriction or changes in eye movements, abnormal posturing (decerebrate, decorticate), changes in reflexes (corneal, gag, deep tendon). The follow-up neurological history and examinations will focus on determination of hard neurological abnormalities: tone, reflexes, movement, posture, interim unprovoked seizures, Neurological

development will be determined by administration of the Malawi Developmental Assessment Test or Kaufman Assessment Battery for children, depending on the age of the subject at the time of enrollment.

Brain swelling intervention: After brain MRI screening, subjects with severely increased brain volume scores (≥ 6) will be eligible for randomization. The parent/ caregiver will be approached for informed consent using the Randomization Consent document. If consent for randomization is granted, randomization assignment will be determined online or opening the next sequentially numbered sealed randomization envelope (stratified by malarial retinopathy status) and the subject's assignment to each of the three study arms determined.

Subjects may be randomized to:

- Arm 1: Usual care + immediate ventilatory support for a maximum of 7 days. These subjects will undergo rapid sequence intubation and be placed on a mechanical ventilator to maintain physiological pCO_2 levels for a maximum of 7 days. Arterial blood gas determinations will take place every 3 hours for the first 24 hours, then every 6 hours until the participant is extubated. Non-scheduled blood gas determinations may occur at the discretion of the PICU physician. Participants will remain in the Pediatric ICU during mechanical ventilation and after its discontinuance.
- Arm 2: Usual care + infusion of 3% hypertonic saline to achieve a target blood concentration of 150-160 mmol/L. Participants will remain in the Pediatric ICU during hypertonic saline infusion. Participants randomized to hypertonic saline administration will have electrolytes evaluated on admission and every six hours thereafter until they regain consciousness ($\text{BCS} \geq 3$)
- Arm 3: Usual care (elevation of the head of the bed 30 degrees and intravenous antimalarial drugs).

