2.2 Agent(s)/Intervention(s)

The goal of this clinical trial is to compare outcomes in children treated with the current standard of care (antimalarial drugs and elevation of the head of the bed 30 degrees) to outcomes in children randomized to receive one of two different approaches to ameliorating the effects of increased brain volume:

- Arm 1: Usual care + immediate mechanical ventilatory support during the initial high risk period, with ventilator withdrawal once brain volume has decreased (brain volume score ≤ 5), and the patient has improved clinically (Blantyre Coma Score ≥ 3).

- Arm 2: Usual care + intravenous hypertonic saline, withdrawn once brain volume has decreased (brain volume score ≤ 5) and the patient has improved clinically (Blantyre Coma Score ≥ 3).
- Arm 3: Usual care (antimalarial drugs plus elevation of the head of the bed by 30 degrees)

Background

The study design was informed by (a) the strong association between increased brain volume and a fatal outcome in pediatric CM, (b) the rapid reversibility of increased brain volume in CM survivors, and (c) the importance of identifying the most feasible intervention for use in malaria-endemic settings.

One challenge is that direct monitoring of intracranial pressure (via intraventricular catheters, or subarachnoid or intraparenchymal bolts) in this setting is relatively contra-indicated --- the risk of infection is too high⁸². Indirect measurements of brain volume are required; the data to date have been derived via MRI. Though the MRI findings are useful and reliable, they are not scalable across sub-Saharan Africa. Consequently, efforts to identify more user-friendly approaches to identifying patients with severely increased brain volume will be evaluated at the same time as this clinical trial is conducted.

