Support for this mechanism of death is based on MRI evidence of severely increased volume in all fatal cases and on clinical observations consistent with pre-morbid brainstem compression and cerebral herniation^{14, 44, 52, 181}. Neuroimaging was required to identify this mechanism: full autopsies with detailed neuropathological studies did not reveal the cause of death in participants with CM. Cerebral edema was a constant feature of all fatal CM cases at autopsy, but gross findings consistent with transtentorial or uncal herniation were less common. This suggests that medullary impingement is a transient event, or that the autopsy itself, performed within 12 hours of death, became effectively a decompressive craniotomy, and may have obscured physical evidence of herniation.

The proposed trial will simultaneously test the hypothesis that increased ICP is the cause of death in children with CM and evaluate two therapeutic approaches: one treatment regimen

targets raised ICP directly and the other targets the effect of ICP (respiratory arrest). If the trial is successful, at least one effective treatment for children with CM at high risk of death will be identified.

The study population

The *mortality rate* in children with CM who have highly increased brain volume (37%) is high enough to support a single-site three-armed clinical trial over six years.

The *survival rate* in this subset (63% survive, and nearly all are discharged within 72 hours of admission) suggests that in survivors, severe edema rapidly subsides spontaneously, and that interventions which (a) reduce edema enough to prevent cerebral herniation or (b) support ventilation during the vulnerable period, might be sufficient to save lives.

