The pathophysiology of intracranial hypertension is complex and depends on the mechanism of cerebral edema, the volume of intracranial contents, the integrity of the BBB, and cerebral perfusion pressure. The balance of Starling forces (the transcapillary hydrostatic pressure gradient that is counterbalanced by an osmotic pressure gradient) determines the magnitude of extracellular fluid flow into the brain substance.

The following issues were considered:

- The etiology of increased brain volume in this patient population has not been established, and the relative contribution of any of the four putative mechanisms, at any single point in the disease process, is unknown. Furthermore, the relative contributions may change over the course of the illness. Since no animal model of CM exists, it is

unlikely that insights into the mechanism of increased brain volume in children with CM will be rapidly forthcoming. Although ongoing research may eventually illuminate the specific mechanisms contributing to the elevated ICP of these patients, our previous work has identified a group of children at high-risk for mortality and broadly effective interventions exist.

- The treatment for increased brain volume that is most likely to be effective in this setting is hypertonic saline.
- Given the rapid reversibility of the increased brain volume, that its etiology is unclear, and that respiratory arrest is the likely cause of death, the other trial arm is ventilatory support.
- Given the high mortality rate in children with CM with highly increased brain volume and the now ready availability of ventilatory support in the ICU in Malawi, those randomized to “usual care” or “hypertonic saline” will receive ‘rescue ventilation’ if they experience a respiratory arrest.

Experimental regimens

Duration of therapy: Serial MRIs have shown that, in survivors, the increased brain volume generally resolves within 48 hours. A summary of data from CM participants on the research ward shows that 85% have either died or been discharged within 72 hours (data not shown). To maximize the chance of observing a positive result, the experimental regimens will continue for 7 days, or until the child experiences death, brain death, or clinical improvement (brain volume score ≤ 5 and Blantyre Coma Score ≥ 3).

Elevation of the head of the bed: In the PICU and PRW, the head of the bed will be elevated to 30°, and the head maintained in the midline with towels.

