 - Continuous monitoring of heart rate and rhythm from EKG, respiratory rate, and pulse oximetry via monitor, and blood pressure via arterial line or cuff. Signals will be archived for offline analyses aimed at identifying heart rate variability patterns over time associated with CM and with clinical improvement or decline in association with treatment.

- Electrolytes and acid-base balance 3-hourly during the first 24 hours and 6-hourly thereafter (in those randomized to hypertonic saline)
- PRW and PICU
 - 2-hourly assessments of vital signs (including temperature) and Blantyre Coma Score until BCS = 5 and temperature is $\leq 37.5^{\circ}\text{C}$ for 24 hours, then 6-hourly.
 - 6-hourly assessments of malaria parasitemia and hematocrit, until two consecutive parasitemia counts are negative.
 - 12-hourly neurological examinations,
 - Daily ophthalmoscopy while unconscious
 - Daily ONSD measurements (while unconscious)
 - Daily TCD examinations
 - Daily MRI examinations (while unconscious if participant is clinically stable for transportation to undergo neuroimaging)

The primary objective (treatment success or failure) will be determined within the first 7 days of hospitalization (Figure 8)

Secondary objectives (Figure 8)

1. The secondary objective involving neurological sequelae at 1, 6, and 12 months after randomization will be determined in survivors randomized in the clinical trial.
2. The secondary objective of identifying surrogate measures of increased brain volume will include participants in the clinical trial as well as study subjects who are screened but do not meet inclusion criteria for clinical trial enrollment e.g. their brain volume is not increased enough to qualify for enrollment in the trial and are therefore not randomized.
3. The secondary objective of assessing the safety of early intubation and mechanical ventilation will include participants in the clinical trial as well as study subjects with CM who are screened but do not meet inclusion criteria for clinical trial enrollment e.g. their brain volume is not increased enough to qualify for enrollment in the trial and are therefore not randomized.
4. TCD endpoints will be determined on all participants (see section 7.2.2.4)]

Choice of participant population and sample size considerations

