1. Arm 1: Usual care + immediate mechanical ventilatory support (VENT) for a maximum of 7 days, with ventilator withdrawal once brain volume has decreased (brain volume score ≤ 5) or the patient has improved clinically (modified Blantyre Coma Score ≥ 3) or the patient dies or meets criteria for severe irreversible neurologic failure.
2. Arm 2: Usual care + intravenous hypertonic saline (HPS) for a maximum of 7 days, withdrawn once brain volume has decreased (brain volume score ≤ 5) and the patient

has improved clinically (Blantyre Coma Score ≥ 3) or the patient dies or meets criteria for severe irreversible neurologic failure.

3. Arm 3: Usual care (UC); intravenous fluids, intravenous artesunate; antipyretics, anticonvulsants and blood transfusions as needed; nutritional support) for a maximum of 7 days, or until brain volume has decreased (brain volume score ≤ 5) and the patient has improved clinically (Blantyre Coma Score ≥ 3) or the patient dies or meets criteria for severe irreversible neurologic failures

Participants will remain in the study throughout their hospitalization and, in survivors, through the 12-month post-randomization follow-up visit. Children are discharged when two sequential 6-hourly blood films are free of malaria parasites, when they have been afebrile for 24 consecutive hours, and when they are able to take medications and food by mouth. Final data collection will be at 12 months post-randomization.

Stratification:

No stratification is required. The ages of retinopathy-positive CM with severely increased brain volume per MRI who survived were compared to those of participants from the same population that died. There was no difference in the age structure (data not shown, $p=0.95$).

Primary and secondary outcomes.

The primary outcome is treatment success or failure, determined within the first 7 days. Treatment success is recovery. Treatment failure is death, ventilatory rescue (for participants in Arms 2 and 3) or meeting criteria for severe irreversible neurologic failure.

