Lactate levels will be determined on admission and every six hours thereafter until the participant has maintained a BCS of 3 for greater than 4 hours. Testing is done with a point of care testing machine. This test uses one drop of blood obtained by finger prick. The monitor will be tested for accuracy on manufacturer supplied test strips every morning.

HIV testing will be performed on all participants, subject to permission being granted by the parent/ guardian present. The test will be performed after recovery of the participant is anticipated by the clinical staff unless test results are thought to have relevance for acute clinical care. Two rapid tests will be performed on a blood sample obtained by finger prick. In the event of discordant results an HIV polymerase chain reaction test will be performed.

Full Blood Count: Participants will have blood drawn for a full blood count (FBC) on admission. FBC includes hemoglobin, hematocrit, RBC indices, white blood cell (WBC) with 5-part differential, and platelet count.

Electrolytes: Participants enrolled in the study who are randomized to hypertonic saline administration will have electrolytes evaluated on admission and every six hours thereafter until they regain consciousness. As this is a crucial measurement in the appropriate administration of the investigational product, a back-up machine will be available.

Respiratory infection screening: On admission, two nasopharyngeal swabs: one for viral identification and one for bacterial detection and quantification by real time PCR. For viral identification we will use the respiratory PCR panel (FilmArray) which includes simultaneous detection of 18 viruses (adenovirus, 4 endemic coronaviruses, SARS-CoV-2, hmpv, RSV, 5 influenza viruses, rhinovirus/enterovirus and 4 parainfluenza viruses). Individual bacterial real time PCR analysis and quantitation will be performed for *Staphylococcus aureus*, *Streptococcus pneumoniae*, *Haemophilus influenzae*, and *Moraxella catarrhalis*.

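### Section 8 ends electrolyte checks in the hypertonic saline arm at waking, although the infusion can continue after waking and Sections 4 and 6.3 set no such stop

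*Combined protocol and SAP*

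**What the plan says.** **Monitoring, Section 8.** Under Arm 2 in Section 8.1, children on HPS have "electrolytes evaluated on admission and every six hours thereafter until they regain consciousness", with consciousness defined as BCS 3 or more. Section 8.2.1 repeats the rule without the BCS definition. Its next sentence justifies a back-up analyser with the words "As this is a crucial measurement in the appropriate administration of the investigational product".

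**Monitoring, Sections 4 and 6.3.** Section 4 (PICU-specific monitoring) sets, for the HPS arm, "Electrolytes and acid-base balance 3-hourly during the first 24 hours and 6-hourly thereafter". Section 6.3 sets serum sodium 3-hourly for 12 hours and then 6-hourly, unless its dosing table directs otherwise. That table (Table 5) gives a recheck time for every sodium band. Neither section mentions waking.

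**When HPS stops.** Section 2.2 describes Arm 2 as "intravenous hypertonic saline, withdrawn once brain volume has decreased" to a score of 5 or less, joined by 'and' to BCS 3 or more. Section 2.3 says "the experimental regimens will continue for 7 days, or until the child experiences death, brain death, or clinical improvement", and defines improvement by the same two conditions together. Section 4 has "intravenous hypertonic saline (HPS) for a maximum of 7 days, withdrawn once brain volume has decreased", again with both conditions, or death or severe irreversible neurologic failure.

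**The concern.** The infusion and its monitoring have different end points. Waking satisfies one of the two conditions for withdrawing HPS, but it ends the Section 8 checks altogether. A clinician working from Section 8 could stop measuring sodium during a sodium infusion and still be following the protocol.

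HPS is titrated to 150-160 mmol/L. Section 6.3 lists five results that hold dosing: sodium above 160 mmol/L, Grade 4 hypokalemia, a pH fall of more than 0.2 within 6 hours, chloride above 125 mmol/L, and osmolality above 340 mOsm. It also has a switch to a chloride/acetate mix, for which one trigger is pH below 7.25. None of these can operate without a measurement. The same is true of the sodium-above-190 SAE in Section 9.2.4.1 and the Section 9.5 halting rule on failure to reach target sodium.

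What is at stake is the safety of individual children and the reliability of those rules, not the primary endpoint or its analysis.

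**Working it through.** The plan gives no figure to reproduce. The check compares the rules and then counts.

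**1. Rules for a child with BCS 3 or more and a brain volume score still 6 or more**

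| Source | HPS | Routine electrolytes or sodium |
|---|---|---|
| 2.2, 2.3, 4 (stopping rule) | continues, up to day 7 | not addressed |
| 4 (monitoring) | – | every 6 h after the first 24 h |
| 6.3, Table 5 | dose set by sodium | every 6 h after 12 h; by band 3 h, 3 h, 6 h or 1 h |
| 8.1, 8.2.1 | – | none |

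**2. Can a child be in this state?** Yes.
- Section 6.7 lets a ventilated child come off at a modified BCS of 4 or more without a repeat MRI. HPS has no such exit.
- Section 4 schedules daily MRI only while the child is unconscious, and Appendix A marks MRI from Day 2 the same way. The score condition may therefore not be reassessed promptly after waking.

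**3. Does it look deliberate?** No. In the same list in 8.1, Arm 1 blood gases run until extubation, that is, to the end of the intervention. Only the HPS arm's monitoring is tied to consciousness. Appendix A has no electrolyte row that would settle the matter.

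**4. Checks per awake day on HPS**
- Sections 4 and 6.3: 24/6 = 4.
- Sections 8.1 and 8.2.1: 0.

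**5. Checks lost per child.** The time on HPS after waking is not in the documents, so these durations are assumed:
- 6 h: 6/6 = 1
- 12 h: 12/6 = 2
- 24 h: 24/6 = 4

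The outer limit comes from the 7-day cap (168 h). If a child wakes at an assumed 24, 48 or 72 h and HPS runs to the cap, 144, 120 or 96 h remain, which is 24, 20 or 16 six-hourly checks. These are ceilings, not expectations.

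**6. How many children?** Not stated. Section 2.3 says that "in survivors, the increased brain volume generally resolves within 48 hours", and that among survivors in this subset "nearly all are discharged within 72 hours of admission". Both suggest few. The upper bound is the arm itself: 3 + 14 + 15 = 32 in the Section 4 projection, of whom 14 + 15 = 29 were projected for 2022-2023.

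**7. Early frequency, nominal checks in the first 24 h**
- Section 4: 24/3 = 8
- Section 6.3: 12/3 + 12/6 = 4 + 2 = 6
- Sections 8.1 and 8.2.1: 24/6 = 4

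The counts are nominal because Table 5 requires a 3-hour recheck whenever sodium is below 150 mmol/L. The scopes also differ: electrolytes with acid-base balance in Section 4, sodium in 6.3, and electrolytes in Section 8.

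**The case against.** The best reply is that this is leftover wording and that other text already keeps the checks going.

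- **Cross-references.** Section 2.4.1.2 promises close electrolyte monitoring and points to 9.2.4, which leads to the sodium dosing table. This shows intent. But 9.2.4 only says what to do once an abnormal value has been found; it sets no routine schedule.
- **SOPs.** Section 6.2 leaves dosage and infusion rates to Standard Operating Procedures, which are not among the documents. They may resolve the point in practice. The protocol text still conflicts, and the SOPs are cited for dosing and rates, not for when testing ends.
- **Hypokalemia.** Section 6.3 holds HPS at Grade 4 hypokalemia, while 9.2.4.2 continues boluses. This is a further inconsistency, but either action needs a potassium result.
- **Event capture and halting.** Section 9.2.1.3 captures listed events for the whole stay, and 9.5 has a sodium-target halting rule. Both presuppose measurement; neither schedules it.
- **Bedside safeguards.** These stand and lower the risk. Under 6.2 the chamber is filled according to weight and current sodium, with only the current amount. HPS is given in the PICU (8.1), where nursing is 1:1 (2.4.2). Staff who follow 6.3 would keep checking.
- **Size.** It is fair to say that the durations after waking are assumed and that no affected child has been identified.
- **Early frequency.** This is the weaker part, because Table 5 narrows the practical difference.

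**Conclusion.** The concern holds. Sections 8.1 and 8.2.1 end electrolyte checks at BCS 3 or more, while the stopping rule can keep HPS running beyond that point. Sections 4 and 6.3 disagree with Section 8, and nothing in the protocol reconciles them. The daily contrast of 4 checks against 0 follows directly from the text. The loss of 1 to 4 checks per child assumes 6 to 24 hours on HPS after waking. The number affected is unknown, probably small, and cannot exceed the HPS arm (32 projected).

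This is a safety-monitoring defect that should be fixed. The differing early frequencies are real but secondary.

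**What to change.** In Sections 8.1 and 8.2.1, replace the stop at regained consciousness with: *until HPS is stopped, on the Section 6.3/Table 5 schedule*. Then choose one early frequency, 3-hourly for 12 hours or for 24 hours, and state it identically in Sections 4, 6.3, 8.1 and 8.2.1. That choice is clinical.

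Neither the HPS stopping rule nor the MRI schedule needs to change.

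The cost is a wording amendment in four sections and about 4 bedside tests per awake day on HPS beyond what Section 8 now requires. Section 6.3 already implies those tests.
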